Methods: Approximately 42 patients, between the ages of 18-65 years, will be consecutively recruited to participate in a randomized prospective clinical trial. Enrolled subjects will be randomly allocated into one of 3 groups: Standard Invisalign therapy (G1-control), Accelerated Invisalign therapy + vibration (G2) and Accelerated Invisalign therapy without vibration (G3). Data collection will include intra oral scans of both the maxillary and mandibular dentition at 5 different time points: TO (baseline), T1 (4 days), T2 (14 days), T3 (6 weeks) and T4 (12 weeks). In addition, PerioPaper strips will be used to sample gingival crevicular fluid at each of the time points listed above. Research subjects will also be asked to complete a daily diary regarding their pain level during treatment. Data analysis will be used to specifically evaluate alignment of adjacent teeth and translational, and/or rotational, tooth movement will be evaluated by superimposing digital models recorded at the specific time points. Inflammation biomarkers will be analyzed with ELISA. Finally, the

statistical significance of our data will be evaluated with a 3 way repeated ANOVA as well as a post hoc comparison with Bonferri correction. P values less than .05 will be considered statistically significant.

Specific Aims:

In this study, we propose a randomized prospective clinical design to investigate effects of vibration therapy, using an AcceleDent Aura® device, on the rate of orthodontic tooth movement, activation of gingival crevicular fluid inflammation biomarkers and patient discomfort in conjunction with accelerated Invisalign therapy.

Hypothesis:

We propose vibration therapy will accelerate orthodontic tooth movement, increase inflammation biomarkers and reduce pain for orthodontic patients.

Background:

Align Technology©, Inc. developed Invisalign® in 1997 to meet the esthetic demands of orthodontic patients and providers. Invisalign patients receive a series of computer-assisted designed stereolithic clear retainers to incrementally resolve their malocclusion. Invisalign® and other advances in orthodontic technology such as clear aligners, ceramic brackets and lingual braces offer options to address the esthetic demands of most orthodontic patients but duration of treatment continues to be one of the most challenging aspects of practice.²

In 2008, OrthoAccel Technologies©, Inc. developed the AcceleDent device to accelerate tooth movement and reduce orthodontic treatment time. Patients receiving vibration therapy are instructed to bite down on the AcceleDent mouthpiece, which vibrates at a .25N (25 grams) force level with a 30 Hz frequency for 20 minutes per day.¹⁵ The theory underlying AcceleDent and the use of vibration to expedite orthodontic tooth movement started in 1892 with the studies of Julius Wollf, who discovered bone adapts to pressure loads.⁵ In 2001, Astronauts in space attempted to use the principles of Wolff's Law to maintain normal bone quality by working out and performing daily tasks while standing on a vibrating plate with the aid of elastic straps.⁶ In 2004, the effect of vibration therapy on bone density was further supported when increased bone density and strength was noted in post-menopausal women who received whole body vibration therapy.⁸ OrthoAccel claims vibration therapy using the AcceleDent device can reduce treatment time up to 50 percent by accelerating the process of bone remodeling required for orthodontic tooth movement.⁹ In 2013, despite relatively little scientific evidence, the FDA approved AcceleDent as a class II medical device and orthodontic accessory to facilitate accelerated tooth movement.

Invisalign therapy in conjunction with AcceleDent has been aggressively marketed towards the esthetically sensitive patient who, not so coincidentally, is the most concerned with duration of treatment. Some orthodontic providers using vibration therapy have deviated from the standard 2-week aligner schedule and recommend a 4-day aligner schedule. Orthodontic patients receiving accelerated Invisalign therapy in conjunction with AcceleDent claim reduced treatment time by as much as 50 percent. What is responsible

for the positive results? The accelerated tooth movement might simply be the result of the accelerated Invisalign therapy, which would raise the question of whether vibration therapy and the cost associated with AcceleDent is justified.

Accelerated orthodontic tooth movement may offer many benefits to both, the patient and the orthodontist. Reduced treatment time reduces the burden of orthodontic treatment by decreasing risk for undesired treatment sequelae (e.g., white spot lesion, caries, gingivitis, etc) and potentially reduces the discomfort commonly associated with orthodontic treatment.¹² Orthodontists benefit from accelerated tooth movement for multiple reasons pertaining to practice management and increased profitability. Orthodontists using accelerated treatment techniques have reported increased profit margins due to reduced chair time and increased organic growth due to differentiation of the practice.²

There are also potential negative outcomes associated with accelerated orthodontic tooth movement. For the patient, there is a potential increased risk for root resorption and increased treatment fees. ² Most orthodontists are charging between \$700-800 for AcceleDent therapy in addition to the normal orthodontic fee. How can Orthodontists expect patients to pay a higher fee over a shorter treatment period? How will this affect the patient's ability to pay?

Further, the mechanism underlying any increased orthodontic tooth movement due to vibration remains unclear. Studies on a cellular level have shown a promising but complicated mechanism of how vibration may enhance activation of various cell proliferation and differentiation molecules within the periodontal ligament (PDL) stem cells as well as increase levels of gingival inflammation biomarkers.¹² For example, vibration therapy might accelerate breakdown of the cellular cytoskeleton, increase actinG trafficking into the nucleus, increase Runx2 gene expression, and thus facilitate bone formation.¹ Whether this mechanotransduction mechanism can be translated into clinical tooth movement is unknown and its clinical evidence remains to be elucidated.

In this study, we propose a randomized prospective clinical design to investigate effects of AcceleDent vibration therapy on the efficiency of tooth movement, on the activation of gingival crevicular fluid biomarkers and on patient discomfort in conjunction with accelerated Invisalign therapy.

Methods:

- 1. Study Design:
 - a. In this study, we propose a single-blinded (Invisalign faculty) randomized prospective paralleled clinical trial to investigate effects of AcceleDent vibration therapy on the efficiency of tooth movement, on the activation of gingival crevicular fluid biomarkers and on patient discomfort in conjunction with accelerated Invisalign therapy. Enrolled subjects will be randomly allocated into one of 3 groups: Standard Invisalign therapy (G1-control), Accelerated Invisalign therapy + vibration (G2) and Accelerated Invisalign therapy without vibration (G3). Patients allocated to the standard Invisalign group will change aligners every 2

weeks while the both intervention groups will change aligners every 4 days. Patients allocated to the vibration group will receive an AcceleDent Aura device and bite down on the mouthpiece for 20 minutes/day. The AcceleDent Aura device vibrates at a .25N (25 grams) force level with a 30 Hz frequency. Data collection will include intra oral scans of both the maxillary and mandibular dentition at 5 different time points: TO (baseline), T1 (4 days), T2 (14 days), T3 (6 weeks) and T4 (12 weeks). In addition, PerioPaper strips will be used to sample gingival crevicular fluid at each of the time points listed above. Research subjects will also be asked to complete a daily diary regarding their pain level during treatment. Treatment plans for enrolled patients will be created using Invisalign's proprietary software: Clincheck Pro®. To reduce treatment plan variability and reduce potential sources of error, [name], who is an "Elite Top 1% Invisalign provider" and also a member of the exclusive North American Invisalign Clinical Advisory Board, will approve each treatment plan. [name] will also be blinded to any patients participation within the study in order to eliminate potential bias.

2. Recruitment:

- a. Participants will be conveniently recruited from the sample population of individuals seeking Invisalign orthodontic therapy within the UNC Graduate Orthodontic Clinic. Benefits for participants will include complementary vibration therapy using the AcceleDent Aura device, which is an estimated value of \$800. Financial reimbursement will also be offered to offset any parking fees associated with the study.
- 3. Power Analysis:
 - a. Our study will have 3 groups for evaluation: G1 control (Invisalign on a 2week aligner schedule) and 2 intervention groups, G2 and G3 (each on an accelerated 4 days aligner schedule). The only difference between the intervention groups will be the use of vibration (G2 with vibration vs G3 without vibration). The expected rate of tooth movement for G1 will be .04mm/day (.25mm/week or .5mm/2 weeks) while the expected rate of tooth movement for G2 and G3 will be .28mm/day (.5mm in 4 days). The standard deviation is assumed 0.1 for three groups. Based on our sample calculation to achieve an adequate power, we will attempt to recruit a total of 42 patients to account for a dropout rate of 30%. Ideally, we would like to have a total sample size of 21 patients to ensure each of 3 study groups will have 7 patients, which will achieve more than 0.8 power even under a Bonferroni correction for multiple comparisons.
- 4. Randomization:
 - a. Our patients will be randomly allocated into the 3 groups based on a block randomization with size 6. The list will be independently generated by our study biostatistician.
- 5. Type I error and statistical significance:
 - a. P values less than .05 will be considered statistically significant in the overall test
- 6. Inclusion Criteria:
 - a. Males or females over the age of 18 years old desiring orthodontic treatment.

- b. Adult dentition with all upper and lower front teeth present and any premolar and molar combination in the upper posterior of two teeth on each side.
- c. Normal pulp vitality and healthy periodontal tissues as determined by intraoral exam.
- d. Good health as determined by medical history.
- e. Willingness and ability to comply with study procedures, attend study visits, and complete the study.
- f. The ability to understand and sign a written informed consent form, which must be signed prior to initiation of study procedures.
- 7. Exclusion Criteria:
 - a. Patient under the age of 18 years old
 - b. Patients diagnosed with systemic diseases such as diabetes, hypertension (high blood pressure), temporomandibular disorders (jaw disorders), or craniofacial syndromes.
 - c. Severe malocclusions that would require adjunctive procedures other than Invisalign. These include impacted teeth, closure of extractions spaces.
 - d. Significant periodontal disease (> 4mm pocket depth or >2 mm of recession on upper anterior teeth).
 - e. Active caries not under care of either a dentist or periodontist.
 - f. Chronic daily use of any non-steroidal anti-inflammatory medication, estrogen, calcitonin, or corticosteroids.
 - **g.** History of use or current use of any bisphosphonate medication or other medication for treatment of osteoporosis.
 - h. Current smoker (must not have smoked in the last 6 months).
 - i. Failing to comply with research protocols
- 8. Arms:
 - a. Control Group (G1): 14 patients, standard Invisalign therapy with 2 week aligner schedule
 - a. Intervention Group (G2): 14 patients, accelerated Invisalign + vibration
 i. AcceleDent device 20 minutes/day per manufacturer's instructions

b. Intervention Group (G3): 14 patients, accelerated Invisalign + no vibration

- 7. Clinical Trial Protocol:
 - a. Visit #1: Clinical Screening with UNC Orthodontic Faculty (clinical purposes only)
 - i. Brief discussion of findings with patient and eligibility for Invisalign
 - b. Visit #2: Clinical exam and records (clinical purposes only), 30 days post visit #1
 - i. Completion of medical history
 - ii. Completion of extra and intra oral exams
 - iii. Completion of alginate impressions
 - iv. Photographs (extra and intra oral)
 - v. Xrays- Panoramic and Cephalometric
 - c. Visit #3: Treatment Plan Presentation (Experimental Baseline), 60 days post visit #1

- i. Clinical Procedures:
 - 1. Treatment plan presentation
 - a. Each treatment plan will be approved by [name] who will be blinded to a patient's study participation
 - 2. Invisalign impressions with PVS material
- ii. Research Procedures:
 - 1. Study recruitment
 - 2. Informed Consent
 - 3. iTero intraoral scan
 - 4. Completion of the Inclusion/Exclusion Case Report Form
- d. Visit #4: (120 days post visit #1/Day #1 of active treatment)
 - i. Clinical Procedures:
 - 1. Intraoral exam and intraoral photographs
 - 2. Deliver aligner number 1 and usage instructions
 - ii. Research Procedures:
 - 1. Deliver AcceleDent Aura device along with instructions
 - 2. Collection of gingival crevicular fluid biomarkers
 - 3. Completion of Faces Pain Scale
 - 4. Deliver daily diaries
- e. Visit #5: (125 days post visit #1/ Day #5 of active treatment)
 - i. Clinical procedures:
 - 1. Deliver aligners 2-4 to accelerate Invisalign groups and aligner schedule instructions
 - ii. Research Procedures:
 - 1. iTero intraoral scan
 - 2. Collection of gingival crevicular fluid biomarkers
 - 3. Completion of Faces Pain Scale and Adverse Event Form
- f. Visit #6: (134 days post visit #1/Day #14 of active treatment)
 - i. Clinical procedures
 - 1. Intraoral exam and intraoral photographs
 - 2. Place attachments (35% phosphoric acid etch, L-pop selfetching primer, composite resin, LED light curing for 30 secs)
 - **3.** Deliver more aligners: 2-3 to control group and 5-11 to intervention groups (accelerated Invisalign)
 - ii. Research Procedures:
 - 1. iTero intraoral scan
 - 2. Collection of gingival crevicular fluid biomarkers
 - 3. Completion of Faces Pain Scale and Adverse Event Form
- g. Visit #7: (176 days post visit #1/6 weeks of after treatment)
 - i. Clinical procedures:
 - 1. Intraoral exam and intraoral photographs

- ii. Deliver more aligners: 4-6 to control group and 11-21 to intervention groups (Accelerated Invisalign)
- h. Research:
 - 1. iTero intraoral scan
 - 2. Collection of gingival crevicular fluid biomarkers
 - 3. Completion of Faces Pain Scale and Adverse Event Form
- i. Visit #8: (218 days post visit #1/12 weeks of active treatment) (End of clinical study)
 - i. Clinical Procedures:
 - 1. Intraoral exam and photographs
 - 2. Deliver more aligners to both control (7-12) and intervention groups (21-30)
 - **3.** Deliver AcceleDent Aura devices to participants in control and non-vibration intervention group.
 - ii. Research Procedures:
 - 1. iTero intraoral scan
 - 2. Collection of gingival crevicular fluid biomarkers
 - 3. Completion of Faces Pain Scale and Adverse Event Form
- j. Visit #9: (260 days post visit #1)
 - i. Clinical Procedures:
 - 1. Intraoral exam and photographs
 - 2. Deliver any remaining aligners
 - 3. iTero Scan for any necessary revisions
- k. Visit #10: (302 days post visit #1)
 - i. Clinical Procedures:
 - 1. Intraoral exam and photographs
 - 2. Deliver revision aligners as needed
- l. Visit #11: Treatment complete, ensure patient satisfaction
 - i. Clinical Procedures:
 - 1. Intraoral exam and photographs
 - 2. Completion of alginate impression
 - 3. Completion of post tx pano and cephalometric xrays
 - 4. Deliver Essix retainers to prevent relapse
- 8. Data Collection:
 - b. 3D intraoral scanning protocol
 - i. T0- baseline
 - ii. T1- 4 days
 - iii. T2-14 days
 - iv. T3-6 weeks
 - v. Tfinal- 12 weeks
 - c. Gingival Crevicular Fluid Sampling
 - i. T0- baseline
 - ii. T1-4 days

- iii. T2-14 days
- iv. T3-6 weeks
- v. Tfinal- 12 weeks
- d. Orthodontic Pain Assessment
 - i. Daily dairy using Faces Pain Scale
- 9. Monitoring Compliance:
 - a. Daily diary usage log
 - b. AcceleDent Fast Trac usage report
- 9. Adverse Events:
 - a. Patients who experience an adverse event or reaction such as: uncontrolled pain or allergy will be disenrolled from the study and allowed to continue Invisalign therapy using the standard two-week aligner schedule. In addition, non-compliant patients will be disenrolled from the study and recommend to continue Invisalign therapy using the standard protocol.
- 10. Data Analysis:
 - a. Tooth leveling and alignment
 - i. Little's Index
 - b. Tooth rotations and translations
 - i. Euler's Law of Motion (6 degrees of freedom)
 - ii. 3D surface mapping
 - c. Alternative measurement options
 - i. Screw Method
 - d. Inflammation biomarkers within gingival crevicular fluid
 - i. ELISA
 - e. Orthodontic Pain Assessment
 - i. Faces Pain Scale
- 11. Statistical Analysis:
 - a. In order to complete statistical analysis for maxillary and mandibular dentition, we will compare the five time points within each group as well as the three groups across each time point.
 - b. Our primary statistical method will be a three-way repeated measurement ANOVA, with the main effects being: vibration, aligner schedule, and time. The ANOVA measurement will identify significant differences within the data and the post hoc comparison will determine which specific variables are involved. In order for a relationship to be considered statistically significant, the p-value must be less than .05.
 - c. One additional method for statistical analysis could be a survival analysis which would be more favorable in the case our study experiences a high volume of drop-outs during treatment.
- 12. Patient Confidentiality:
 - a. Records related to this research study that involve perennial information will only be accessible by the primary research committee and direct assistants. Records will be stored on encrypted, password-protected computer hard drives. A 3-digit code number will be used rather than the subject's name to identify the specific data related to his/her involvement in the study. Only the research investigators will have access to the file that links personal

information to the 3-digit codes, and this file will be stored in a separate location from the actual research data.

Project Timeline:

Item	Date
Study Design; IRB submission ([name])	Spring 2016
Background Research	March 2016
Loose conceptual framework	March 2016
Presentation	April 2, 2016
Protocol	May 16, 2016
IRB approval	May 2016
Select study population	August 2016
Clinical Trial	November 2016

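### Bonferroni for the post hoc comparisons is valid but needlessly conservative; Holm holds the same error rate and is never less powerful

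*Combined protocol and SAP*

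**What the plan says.** - Abstract, Methods: a three-way repeated ANOVA together with a "post hoc comparison with Bonferri correction".
- Section 5 (Type I error): "P values less than .05 will be considered statistically significant in the overall test".
- Section 3 (Power Analysis): "each of 3 study groups will have 7 patients, which will achieve more than 0.8 power even under a Bonferroni correction for multiple comparisons". The inputs are .04 mm/day for G1, .28 mm/day for G2 and G3 (glossed in brackets as .5 mm in 4 days), and "The standard deviation is assumed 0.1 for three groups". G2 and G3 have the same expected rate.
- Section 8 (Arms): 14 patients enrolled per group.
- Section 11 (Statistical Analysis): the ANOVA factors are vibration, aligner schedule and time. Time points are to be compared within each group, and groups at each time point. The post hoc comparison is described as following the ANOVA, but a significant overall test is not stated as a condition for it.

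No section says how many comparisons the Bonferroni correction divides by.

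**The concern.** The trial's main question is whether vibration adds anything to the faster aligner schedule, which is G2 vs G3. The plan sets no effect size for that contrast, and each arm will have between 7 and 14 patients. Power given up through the choice of correction is therefore worth recovering if it costs no patients and no error control. Bonferroni holds every pair to .05/3 = .0167, whatever the other pairs show. A step-down rule relaxes the threshold once the clearest difference has been declared. That helps here because the contrasts with G1 are expected to be the larger ones.

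**Working it through.** **Inputs.** From Section 3: SD .1; rates .04 (G1) and .28 (G2, G3); 7 per group. From Section 8: 14 per group. The bracketed .5 mm in 4 days is .5/4 = .125 mm/day, which does not agree with .28, so G3 is run at both values. Two-sided tests and a vibration gain of .08 mm/day are my assumptions.

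**Formula.** For one pair with pooled variance, power = P(|T| > t(1 − α/2; df)), where T is noncentral t, df = 3(n − 1) and noncentrality = (difference/SD) × √(n/2).

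**1. The plan's own figure.** With n = 7 and difference .28 − .04 = .24, noncentrality is 2.4 × √3.5 = 4.49. At α = .05/3 and df 18 the critical value is 2.639 and power is 0.958 (0.938 for a two-sample t test with df 12). The claim of more than 0.8 is met for G1 against either accelerated group.

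**2. Bounds for G2 vs G3 with a gain of .08.** Noncentrality is .8 × √3.5 = 1.497 at n = 7 and .8 × √7 = 2.117 at n = 14.

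| n per arm | Power at .05/3 | Power at .05 |
|---|---|---|
| 7 | 0.155 | 0.294 |
| 14 | 0.361 | 0.542 |

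Holm must lie between the two columns.

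**3. Holm.** Order the three p-values. Compare the smallest with .05/3, the next with .05/2 and the largest with .05, and stop at the first failure. Simulated power for G2 vs G3 (400,000 three-arm trials per row):

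| Means G1 / G3 / G2 | n | Bonferroni | Holm |
|---|---|---|---|
| .04 / .125 / .205 | 7 | 0.155 | 0.206 |
| .04 / .125 / .205 | 14 | 0.362 | 0.475 |
| .04 / .28 / .36 | 7 | 0.155 | 0.290 |
| .04 / .28 / .36 | 14 | 0.360 | 0.540 |
| .04 / .04 / .12 (no schedule effect) | 7 | 0.155 | 0.168 |
| .04 / .04 / .12 (no schedule effect) | 14 | 0.361 | 0.387 |

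The gain is about 5 to 13 points at n = 7 and 11 to 18 at n = 14 when the schedule has an effect. It is about 1 and 3 points when it has none. At the plan's stated .04 / .28 / .28 with n = 7, power for a contrast with G1 goes from 0.958 to 0.970, about 1 point.

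**4. Error rate.** With all three means equal, family-wise error is 0.042 for both rules at n = 7. With G1 far away and G2 = G3 (.04 / .28 / .28), the chance of a false G2 vs G3 finding is 0.017 with Bonferroni and 0.047 with Holm. Both stay within .05.

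**5. What the overall test costs.** Requiring a significant one-way F test before the Bonferroni pairs lowers power by at most about 0.4 points in the configurations searched, and by under 0.01 points at the plan's stated inputs.

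**6. The family in Section 11.** Five time points give 10 pairs within each of three groups, and three groups give 3 pairs at each of five times: 3 × 10 + 5 × 3 = 45 comparisons per outcome. If the overall ANOVA is passed through a time effect and group pairs are then tested at .05 each, family-wise error is 0.12 at one time point. Over five time points it is 0.28 to 0.47 (within-patient correlation 0.8 down to 0, assumed).

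**The case against.** The strongest case for leaving the plan alone is that Bonferroni is valid, the trial was sized with it in mind, and at the plan's stated rates the difference is about 1 point. The larger gains rest on a vibration effect that the plan does not give, and they shrink to 1 to 3 points if the schedule has no effect. Even with Holm, G2 vs G3 stays below 0.55 in every scenario above. All of this stands. It limits the size of the point, but it gives no reason to prefer Bonferroni, because Holm is never worse on power and needs no further assumption.

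Two stronger readings are tempting, and the documents support neither:

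- **Correcting twice.** A reader might infer that an overall test at .05 followed by Bonferroni is a double penalty. The overall test costs almost nothing (step 5), and the plan only implies that it acts as a gate. The loss comes from .05/3 in place of .05.
- **No protection added.** With exactly three groups and one three-group F test, unadjusted pairs after a significant F do hold family-wise error at .05 (0.050 in simulation), so a reader might infer that Bonferroni is redundant. The planned analysis is not that test. It includes time as a factor and up to 45 comparisons per outcome, and there unadjusted pairs would inflate the error (step 6).

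**Conclusion.** The point holds as a minor matter of efficiency. The plan's Bonferroni correction controls error, and its stated power under Bonferroni reproduces for the contrasts with G1. Holm would give the same control with more power where it matters most: roughly 5 to 18 points for G2 vs G3 between 7 and 14 per arm if the schedule has an effect, and 1 to 3 points if it has none. These figures rest on the plan's SD of .1, the assumed gain of .08 mm/day, two-sided pooled t tests, and a family of the three group pairs at one time point. They do not give the gain for the wider family in Section 11. The 18 points should not be read as a typical loss: it is close to the maximum over effect sizes. The change does not rescue an underpowered vibration contrast.

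**What to change.** In the abstract and in Section 11, replace Bonferroni with Holm for the post hoc comparisons, and list which comparisons form the family. Section 3's power statement can stay as a conservative figure. The cost is a sentence or two and no patients. The small drawback is that simultaneous confidence intervals matching Holm are less simple than Bonferroni intervals, so the plan should say which intervals will be reported.

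Optionally, the sponsor could prespecify one 2-df test of the three groups on change to T4 and, only if it is significant, test each of the three pairs at .05. With means .04 / .125 / .205 this gives G2 vs G3 power of 0.28 at 7 per arm and 0.54 at 14. It requires adding a test that the plan does not now contain. It must not be extended to pairs tested after the three-way ANOVA or across time points.

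### The stated blinding covers only the treatment-plan approver; nothing masks the reading of the tooth-movement scans, which matters most for vibration versus no vibration (G2 versus G3)

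*Combined protocol and SAP*

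**What the plan says.** Section 1 (Study Design) calls the trial a "single-blinded (Invisalign faculty) randomized prospective paralleled clinical trial". The same section explains the role of the blinded person, who "will approve each treatment plan" and "will also be blinded to any patients participation within the study in order to eliminate potential bias". Section 7 (Clinical Trial Protocol), visit #3, repeats that each plan is approved by this person, "who will be blinded to a patient's study participation". Visit #3 comes before active treatment and before every follow-up scan.

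The outcome is read later. The Abstract (Methods) says that "tooth movement will be evaluated by superimposing digital models recorded at the specific time points". Section 10 (Data Analysis) lists "Little's Index", six-degree-of-freedom rotations and translations, and 3D surface mapping. Neither place names the person who measures or says that the arm is hidden.

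The nearest thing to a safeguard is in section 12 (Patient Confidentiality): "A 3-digit code number will be used rather than the subject's name to identify the specific data". The research investigators hold the file that links code to person.

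**The concern.** Blinding the plan approver prevents knowledge of trial participation from influencing the programmed tooth movement. It does not reach the later step at which tooth movement is measured. Superimposing models and scoring an alignment index both involve some judgement, and the plan leaves open that this is done by someone who knows the arm.

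The contrast most exposed is G2 versus G3. Section 3 (Power Analysis) says these arms differ only in vibration and gives them the same expected rate. The Hypothesis says vibration will accelerate movement. A measurer who knows both the arm and the hypothesis could, without intending to, produce a small difference where the plan's own planning figures predict none. This contrast also answers the question posed in the Background: whether vibration adds anything to the faster aligner schedule. No sham device is described, so patients will know whether they have one. Reading the scans is a step at which masking is still feasible.

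**Working it through.** **1. Who is masked, and at which step**

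| Step | Where | Masking stated |
|---|---|---|
| Treatment-plan approval | Sections 1 and 7, visit #3 | Yes, to study participation |
| Allocation list | Section 4 | Generated independently by the biostatistician; concerns allocation, not measurement |
| Superimposition of scans | Abstract (Methods), section 10 | None; assessor not named |
| Alignment index, rotations, surface mapping | Section 10 | None; assessor not named |
| Data coding | Section 12 | Code replaces the name; not said to hide the arm |

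**2. The plan's own figure**

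Section 3 claims power above 0.8 with 7 per group under a Bonferroni correction. Its inputs are G1 at .04 and G2/G3 at .28 mm/day (difference .24) and SD .1 (unit not given; taken as mm/day). The noncentrality is .24 / (.1 × √(2/7)) = 4.49. At two-sided alpha .05/3 with 12 df, the critical t is 2.78 and power is 0.94. The claim reproduces from these inputs. It concerns G1 against the accelerated arms. For G2 versus G3 the planned difference is .28 − .28 = 0.

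**3. What a reading bias would do to G2 versus G3**

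The documents give no measurement error, so the shift b is an assumption: .01 to .02 mm/day in favour of vibration. Other inputs are a true difference of 0, SD .1 (section 3) and two-sided alpha .05 (sidedness assumed). The arm sizes are 7 (section 3 target), 14 (section 8, Arms) and 10, since 14 × 0.7 = 9.8 after the stated 30% dropout.

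Noncentrality = b / (SD × √(2/n)), with df = 2n − 2. The false-positive rate is the probability that a noncentral t exceeds the critical value in either direction. For example, with n = 14 and b = .02: .02 / (.1 × √(2/14)) = 0.529, and the rate is 8.0%.

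| n per arm | b = 0 | b = .01 | b = .02 |
|---|---|---|---|
| 7 | 5.0% | 5.3% | 6.4% |
| 10 | 5.0% | 5.5% | 7.1% |
| 14 | 5.0% | 5.7% | 8.0% |

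At alpha .05/3, b = .02 gives 2.3%, 2.6% and 3.1% for n = 7, 10 and 14, against 1.7% with no bias.

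**4. How large the assumed shift is**

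Over 4 days, .01 to .02 mm/day is 0.04 to 0.08 mm. Over 12 weeks (84 days) it is 0.84 to 1.68 mm. The range is therefore already generous for the 12-week reading.

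The two-sample t-test is a simplification of the planned three-way repeated-measures ANOVA and serves only to show scale.

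**The case against.** The strongest reply is that the documents are silent about the assessor, and silence is not a decision to measure unmasked. That stands. A reader might infer that the plan prescribes unblinded reading, or that the approver has no part in measurement. The text supports neither; it only leaves the point open. It would also be unfair to call the approver's masking misdirected. It protects a real source of bias, and masked measurement should be added to it rather than replace it.

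A reader might also infer that the primary endpoint is compromised. No endpoint is formally named as primary. Tooth-movement rate is the first-listed outcome and the basis of the power calculation, and the point should go no further than that.

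Nor do the documents support a large inflation of false positives. With 10 per arm, the same shift gives about 14-40% if the SD is taken as .025, but the only SD stated is .1.

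Finally, masking would be incomplete. Attachments bonded at visit #6 can reveal the time point. The amount of movement may separate G1 from the accelerated arms. A measurer who also treats patients may recognise a dentition. The self-reported pain diary is not protected at all. These limits stand, but the vibration contrast remains maskable, because nothing described in the plan would make a G2 scan look different from a G3 scan.

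**Conclusion.** The point holds as a gap that is cheap to close. The stated blinding reaches plan approval only, the confidentiality code does not mask the arm, and the plan therefore permits unmasked reading of the tooth-movement outcome. The likely statistical effect is modest: about 5-8% false positives instead of 5% for G2 versus G3. That figure assumes a systematic shift of .01 to .02 mm/day, SD .1, 7 to 14 per arm and an unadjusted two-sided 5% test. The recommendation rests less on this number than on the direction of the risk. Any such bias would favour the hypothesis in the contrast where the power section expects no difference, and it can be avoided without altering sample size, visits or treatment.

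**What to change.** Keep the plan approver masked, and add the following to sections 1 and 10:

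- Name the role that measures the scans and state that this person is masked to arm.
- Have someone who measures no outcomes, for example the biostatistician, relabel the exported scans with random codes that hide the arm. Each patient's scans stay linked to that patient's baseline so that superimposition is possible.
- The existing measurer works only from coded files. Codes are opened after all measurements are locked.
- Gingival crevicular fluid tubes can be coded in the same way at little cost.
- State the limits of the masking given above, and that its main gain is for G2 versus G3.

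The cost is some relabelling of files and tubes. No extra assessor is required, although recognition of dentitions remains possible if the measurer also treats patients.
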